## 10 CHANGE FROM THE PROTOCOL

The planned analyses below were not done.

- Summary of AEs by SOC, Preferred Term and severity of event
- Summary of the change from baseline for vital signs, 12-lead ECG and routine safety laboratory tests
- A linear mixed model analysis for log-transformed PK parameters
- All analyses for Part 4 or 5

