## Europe/Mitsubishi Tanabe Pharma Europe Ltd

## STUDY PROTOCOL

	
Statistical methods:	
Sample size:  The sample size is not based on a formal statistical evaluation but was considered to be adequate to meet the objectives of the study and is a typical size for first-in-man SAD and MAD studies. A sufficient number of subjects will be screened to ensure that the planned sample size will be achieved.
 
Safety evaluation  AEs will be considered as treatment-emergent if they occur on or after the first dose administration of IMP or if a pre-dose event increases in severity following dosing. The frequency and incidence of treatment-emergent AEs (TEAEs) will be summarised by System Organ Class and Preferred Term for each dose level and by fed state, gender and race category where appropriate. Summaries will also be presented by relationship to treatment and severity of event. Serious TEAEs and TEAEs leading to discontinuation will be listed.  Safety laboratory test results, vital signs, and ECG parameters will be summarised by planned sampling point and for each dose level and by fed state, gender and race category where appropriate. Other safety measurements will be summarised and/or listed according to the data type.
 
Pharmacokinetic data  All data will be listed.
 
(i) Plasma and urine concentration of MT-6345  Plasma MT-6345 concentrations will be summarised by dose level, planned time point and by fed state, gender and race where appropriate using descriptive statistics.  By-subject plasma concentration versus time will be plotted as well as the mean concentration, for each dose level, and by fed state, gender and race where appropriate, using linear and semi-logarithmic scales. The concentration of MT-6345 in urine will be listed for Part 3.
 
(ii) Urine pharmacokinetic parameters of MT-6345  Urinary excretion and percent urinary excretion during each collection interval will be listed. Ae, Ae% and CLR will be summarised by dose level where appropriate, using descriptive statistics.
 
(iii) Plasma pharmacokinetic parameters of MT-6345  The PK parameters will be derived by non-compartmental analysis using WinNonlin® software (version 6.2 or later).  The PK parameters will be summarised for each dose level and by fed state, gender and race category where appropriate and time of dosing using descriptive statistics.
 
(iv) Dose proportionality (Part 1)  The PK parameters (AUC0-∞, AUC0-last and Cmax) from the SAD part will be used in the exploration of dose proportionality. The overall dose proportionality will first be evaluated using the power model. A linear model will be used to fit the power model, after log-transformation of the parameter of interest (e.g., AUC [AUC0-∞, AUC0-last] or Cmax). The model will include the log-transformed dose as fixed effect.

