#### **4.7 Study stopping criteria**

The study will be stopped if either of the following occur:

1. A 'serious' adverse reaction (i.e., an SAE considered at least possibly related to the IMP administration) in 1 subject.
2. 'Severe' non-serious adverse reactions (i.e., severe non-serious AEs considered as, at least, possibly related to the IMP administration) in 2 subjects administered with MT-6345 in the same cohort, independent of whether or not the event is within the same System Organ Class (SOC).

Whether the event was related to the IMP administration will be determined by the Investigator. If the study is halted, a temporary halt will be submitted to the Medicines and Healthcare products Regulatory Agency (MHRA) and IEC in the form of a substantial amendment. The study may be

Europe/Mitsubishi Tanabe Pharma Europe Ltd  
STUDY PROTOCOL

---

resumed or terminated; however, it will not be resumed until a further substantial amendment to resume the study is submitted and approved by the MHRA and IEC.

Details on the process for confirming the above criteria, and any necessary actions, will be contained within a study-specific Safety Monitoring Plan.

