#### 2.1.3. [REDACTED]

### 2.2. Study Endpoints

#### 2.2.1. Primary Endpoints

##### Safety assessments

- Incidence and severity of adverse events (AEs).

- Vital signs (supine blood pressure, pulse rate, respiratory rate and oral body temperature).
- ECG parameters (including heart rate and cardiac intervals: PR, QRS, QT and calculation of corrected QT interval using Fridericia's formula [QTcF]).
- Clinical laboratory assessments (including haematology, biochemistry, coagulation and urinalysis).
- Physical examination.
- Part 3 only, in addition: specialist eye examination findings

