### 7.3 Data Handling Convention for Missing Data

#### (1) Non-PK related

Adverse events:

If severity or relationship is found to be missing, the most severe occurrence will be imputed for the summary of interest.

For missing or partial AE start dates, the AE will be treated as a TEAE if it cannot be determined to be a non-TEAE. Adverse events with unknown start and/or end times (but where the date is known) will be imputed with a time of 23.59 h for the tabulations but will be shown as NK:NK in the listings (where NK = Not Known)

Other Safety-related endpoints:

For other safety-related summaries, only observed data will be used. Unless otherwise specified, missing safety data will not be imputed.

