### **8.2.1 Adverse Events**

An overall summary including the following will be presented by study part.

- Subjects with at least one TEAE
- Subjects with at least one TESAE
- Subjects with at least one adverse drug reaction
- Subjects with at least one TEAE leading to discontinuation of study drug

The following summaries also will be conducted.

- TEAEs by SOC and PT
- TEAEs by SOC, PT and relationship to study drug

Each of the summaries will be done at the subject level - multiple occurrences of the same event within a subject will be counted once in the summaries by SOC and PT; multiple occurrences of the same event within a subject will be counted once in the maximum severity category (severe > moderate > mild) and/or maximum drug relationship category (reasonable possibility/no reasonable possibility). If intensity or relationship is found to be missing, the most severe occurrence will be imputed for that particular summary.

All AEs will be listed.

The above TEAE summaries will be produced for each dose level and placebo. For Part 2, all TEAEs will be tabulated in incidence tables by treatment (MT-6435 or placebo) as described above by fasting status. For subjects in Part 2, any AEs occurring in the first (fasting) period during Part 1 will be assigned to Part 1 until the time of dosing in Part 2. Therefore any AEs that occur during the washout period will be assigned to Part 1.

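### AE severity stays in the first primary endpoint, but the SAP drops the only summary that would show it by dose level; the Part 2 baseline and the change-from-baseline summaries need smaller repairs

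*SAP*

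**What the plan says.** **Endpoint.** SAP 2.2.1 opens its list of primary endpoints with "Incidence and severity of adverse events (AEs"), as protocol 2.2.1 does.

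**Planned summaries.** Protocol 10.3.4.1 plans three TEAE summaries: by SOC and Preferred Term, by those plus severity, and by those plus relationship. The synopsis makes the same commitment: "Summaries will also be presented by relationship to treatment and severity of event".

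**What the SAP keeps.** SAP 8.2.1 has an overall summary with four rows, a SOC and PT table, and "TEAEs by SOC, PT and relationship to study drug". Section 10 lists "Summary of AEs by SOC, Preferred Term and severity of event" as not done. It says the same of "Summary of the change from baseline for vital signs, 12-lead ECG and routine safety laboratory tests". It gives no reason for either.

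**Rules that remain.** SAP 8.2.1 says that repeated events are "counted once in the maximum severity category (severe > moderate > mild) and/or maximum drug relationship category". SAP 7.3 says: "If severity or relationship is found to be missing, the most severe occurrence will be imputed for the summary of interest".

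**Baseline.** SAP 7.2 takes the last value observed before study drug is first taken, unscheduled visits included, unless specified otherwise. Protocol 10.3.4.2 instead used the last valid Day 1 value before dosing for vital signs and ECG. SAP Section 1 says that its statistical details override the protocol's.

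**The concern.** The primary objective is safety and tolerability, and severity is one of the two things that the first primary endpoint names. If no table shows mild, moderate and severe events by dose level against placebo, the report can summarise incidence but not severity. A reader who wants to know whether events became more severe as the dose rose must count them from a listing.

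The other two points affect how change is described. A baseline carried over from Part 1 could move a returning subject into or out of a QTcF-increase category in the fed period. Without change-from-baseline summaries, the tables cannot show how widely individual subjects moved.

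**Working it through.** No sample-size or error-rate calculation applies: the sample size has no formal basis (SAP 3.3.1) and the safety analysis is descriptive. The check sets the sections side by side.

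**1. AE outputs**

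| Output | Protocol 10.3.4.1 | SAP |
|---|---|---|
| TEAEs by SOC and PT | planned | kept (8.2.1) |
| TEAEs by SOC, PT and severity | planned | dropped (Section 10) |
| TEAEs by SOC, PT and relationship | planned | kept (8.2.1) |
| Overall summary, four rows | not listed | added (8.2.1) |

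Tables: 3 planned − 1 dropped = 2 kept. Outputs: 2 tables + 1 overall summary = 3. Outputs that split by severity: 1 planned, 0 left.

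The four overall rows count subjects with any TEAE, any serious TEAE, any adverse drug reaction, and any TEAE leading to discontinuation of study drug. The serious row cannot stand in for severity, because protocol 8.3 states that serious and severe mean different things.

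**2. Subjects concerned.** SAP 3.3.2 gives 44 in Part 1 and 8 in Part 3: 44 + 8 = 52, as stated. Six Part 1 subjects returned for Part 2 and are not counted again.

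**3. Leftover rules.** The counting rule in 8.2.1 and the imputation rule in 7.3 treat severity and relationship together. The relationship half serves the retained relationship table. The severity half has no named table to serve.

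**4. Part 2 baseline.** Returning subjects first took study drug in Part 1. Under the literal wording of SAP 7.2, their baseline is therefore the Part 1 pre-dose value. SAP 3.1.1 sets at least 15 days between the Part 1 and Part 2 doses, so in the fed period that value is at least 15 days old. The retained output that uses it is the count of QTcF increases above 30 and 60 msec (SAP 7.1.2.3 and 8.2.4). At most 6 subjects are affected, active and placebo together; the split is not given.

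**5. Change from baseline.** Protocol 10.3.4.2 and 10.3.4.3 plan change summaries for vital signs, ECG and laboratory variables. SAP 8.2.2 to 8.2.4 tabulate absolute values. What those tables allow is:

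- Mean change = mean at visit − mean at baseline, if the same subjects contribute to both rows. The mean shift is usually recoverable. It is not where a subject's baseline is an unscheduled value, since 7.2 admits such values while 6.1 and 9.3 keep them out of the by-visit tables.
- Var(change) = Var(visit) + Var(baseline) − 2 Cov(visit, baseline). The tables give the two variances but not the covariance, so the SD of change cannot be derived. Nor can the minimum and maximum change.

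Some information on change survives: the QTcF-increase counts, the overall evaluation of vital signs and ECG, and clinically significant abnormalities, which reach the TEAE tables because they are recorded as AEs (protocol 6.5.2, 6.5.3 and 8.5).

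**The case against.** The strongest reply is that nothing is hidden or lost. Section 10 declares both omissions, and the SAP overrides the protocol. All AEs are listed, and protocol 10.3.4.1 puts severity, dose level and relationship in that listing. With 52 subjects in small cohorts and no inferential safety analysis, severity by dose can be counted by hand. All of this is correct. It limits the point to a missing summary, but a listing is still not a summary by dose level and placebo.

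The SAP also says that assessments not performed are greyed out. Shading cannot be seen in the text reviewed, so some leftover wording may be marked as inactive. SAP 3.1.2 adds that termination left some assessments undone in Parts 1 to 3. Neither remark explains the gap, because AEs were collected and are still tabulated in other ways.

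On Part 2, other text suggests that the sponsor thinks period by period: there are fed and fasted columns (9.2), a Day 1 pre-dose row for Parts 1 and 2 (9.3), and AE attribution by period (8.2.1). That makes a per-period baseline the likely intention, but 7.2 does not say so.

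A reader might draw three stronger conclusions that the documents do not support:

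- *That the stopping rule in protocol 4.7 depends on this table.* Criterion 2 concerns "severe non-serious AEs considered as, at least, possibly related to the IMP administration" in two subjects of one cohort. It is applied during the study, with relatedness judged by the Investigator. A final table by SOC, PT and severity would not show it, since it does not cross severity with relationship.
- *That the deletions were never justified.* The SAP gives no reason, but protocol 10.3.1 places justification in a separate document and the clinical study report.
- *That all information on change from baseline is gone.* It is partly covered, as step 5 shows.

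**Conclusion.** The point holds as a gap in presentation that should be fixed. Severity, a named component of the first primary endpoint, has no summary in any of the three remaining AE outputs, although rules for counting and imputing it are still in the SAP. This rests on reading 8.2.1 and Section 10 together, and they agree. It does not mean that severity data are missing or that the change was concealed.

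The Part 2 baseline is a wording fault that affects at most 6 subjects in one categorical output, and it depends on a literal reading of 7.2. The loss of the continuous change summaries is the least of the three: the SD and range of individual changes are lost from the tables, while mean shifts are mostly recoverable and the main outliers are partly covered.

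**What to change.** 1. In SAP 8.2.1, restore a table of TEAEs by SOC, PT and maximum severity, by dose level and placebo for Parts 1 to 3, and by fed state for Part 2. Delete the first bullet of Section 10. The counting and imputation rules in 8.2.1 and 7.3 then serve a table again.
2. In SAP 7.2, define baseline as the last value before dosing in each treatment period.
3. In SAP 8.2.2 to 8.2.4, add change-from-baseline columns beside the absolute values, using the formula already in 6.1. Delete the second bullet of Section 10.

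The cost is a few sentences of SAP text and a few more descriptive tables from data already collected. No new data and no inferential analysis are needed.

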**10.3 Statistical analysis****10.3.1 General considerations**

The SAP, containing detailed data handling, analysis methods, outputs (tables, figures and listings), will be developed and approved prior to database lock. Additional analysis may be performed if deemed necessary. Any deviations from the planned analysis will be described and justified in a separate document and in the Clinical Study Report (CSR).

All subjects who received placebo for Part 1 will be pooled into a single placebo group (dose level 0) and all subjects who received placebo for Part 3 will be pooled into a single placebo group (dose level 0) for the final statistical analysis. The assignment of subjects to the various analysis sets will be listed and summarised. Summaries for Parts 2, 4 and 5 will be done by treatment group and by status, with corresponding dose cohort from Part 1.

STUDY PROTOCOL

---

All variables will be summarised by treatment group/cohort. Unless otherwise stated, continuous data will be summarised descriptively using N (number of subjects), n (number of observations), mean, standard deviation (SD), minimum, median and maximum. Categorical data will be summarised using frequency tables (frequency and percentage). The term "log-transformation" refers to the natural logarithmic transformation throughout the SAP.

All individual subject data will be listed.

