#### **10.3.5.5 Food effect (Part 2)**

A linear mixed model will be used to analyse log-transformed  $AUC_{0-\infty}$ ,  $AUC_{0-last}$  and  $C_{max}$ , with fed state (fed, fasted) as fixed effects and subject as a random effect. Difference in least square (LS) means and corresponding 90% CI will be back-transformed to obtain the estimate and CI of geometric mean ratio of fed to fasted. The reference treatment will be the corresponding dose from Part 1.

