#### **10.3.5.9 Gender effect (Part 4)**

A linear model will be used to analyse log-transformed  $AUC_{0-\infty}$ ,  $AUC_{0-last}$  and  $C_{max}$ , with gender (male, female) as fixed effects. Difference in LS means and corresponding 90% CI will be back-transformed to obtain the estimate and CI of geometric mean ratio comparing female to male. The reference treatment will be the corresponding dose from Part 1.

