## 1. INTRODUCTION

This statistical analysis plan (SAP) is based on the final protocol (v2.0) dated 12-DEC-2018. The plan covers statistical analysis, tabulations and listings of the study data to investigate the safety, tolerability and pharmacokinetics of single and multiple ascending doses of MT-6345 compared to placebo in healthy subjects.

Any statistical analysis details described in this document supersede any description of statistical analysis in the protocol.

This study was terminated due to brain changes in male rats in the 13-week tox study. Subjects were enrolled in only Part 1, Part 2 and Part 3. Some assessments which were not performed are grayed out in this SAP.

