#### 2.1.2. Secondary Objectives

- To investigate the PK profile of MT-6345 following single and multiple ascending oral doses administered to healthy male subjects.
- To investigate the effect of food ~~and/or~~ on the PK profile of MT-6345 following a single oral dose administered to healthy male subjects.
- To investigate the effect of gender on the PK profile of MT-6345 following a single oral dose administered to healthy female subjects.
- To investigate the effect of MT-6345 drug concentration on QT prolongation and QTc interval following single and multiple oral doses administered to healthy subjects.

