#### **3.3.2. Actual Sample Size**

This study was terminated due to brain changes in male rats in the 13-week tox study. Subjects were enrolled in only Part 1, Part 2 and Part 3. 52 subjects were actually randomized as follows.

Part 1: 44 subjects in total; 8 subjects for [REDACTED] and [REDACTED] cohorts respectively, and 6 subjects for [REDACTED] and [REDACTED] cohorts, respectively.

Part 2: 6 subjects returned to received the same [REDACTED] dose as in Part 1 (active or placebo), are therefore not unique patients and are not counted again in the total number of exposed subjects.

Part 3: 8 subjects in the [REDACTED] cohort

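### SAP Section 10 drops the food-effect model, so Part 2, which was run, has no planned fed/fasted ratio or confidence interval

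*SAP*

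**What the plan says.** Protocol 10.3.5.5 covers the food effect: "A linear mixed model will be used to analyse log-transformed" AUC0-∞, AUC0-last and Cmax, with fed state fixed and subject random. The difference in least-squares means is back-transformed to a fed/fasted geometric mean ratio with a 90% CI. The gender analysis (10.3.5.9) is worded differently: "A linear model will be used to analyse log-transformed" the same parameters, with no random effect. The race analysis (10.3.5.10) follows the gender wording.

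SAP Section 10 lists planned analyses that were not done. One bullet is "A linear mixed model analysis for log-transformed PK parameters". A separate bullet reads "All analyses for Part 4 or 5". SAP Section 1 settles which document governs: "Any statistical analysis details described in this document supersede any description of statistical analysis in the protocol".

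SAP 2.1.2 still contains the objective "To investigate the effect of food" on the PK profile. SAP 3.3.2 records that in Part 2 "6 subjects returned to received the same" dose as in Part 1, active or placebo. It does not give the split.

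**The concern.** Part 2 was included to measure the effect of food, and each returning active subject supplies a fed and a fasted profile. With the mixed model gone, no planned output gives the size of that effect or its uncertainty. A reader who wants either must derive it from the listings and make their own choice of subjects and method. Two readers could then report different food effects from the same trial, neither of them prespecified.

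**Working it through.** **Step 1. Which model was dropped?** The protocol's only mixed model for PK parameters is in 10.3.5.5. Dose proportionality (10.3.5.4, 10.3.5.6), gender and race all use a linear model without a random effect, and Parts 4 and 5 have their own bullet in SAP Section 10. The mixed-model bullet is therefore the food-effect analysis.

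**Step 2. Does it survive elsewhere?** SAP 8.3 has sections on concentrations, parameters, dose proportionality and steady state, but none on food effect. Because the SAP supersedes the protocol's statistics, 10.3.5.5 does not apply by default.

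**Step 3. What remains?** Three kinds of output remain:
- PK parameters summarised by fed state and listed by part (8.3.2), with geometric mean and geometric CV% (6.1)
- plots overlaid by food state (8.3.1)
- fed and fasted table and listing layouts (9.2)

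A crude ratio can be formed by hand from two geometric means. A paired interval cannot be formed from the summary table.

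**Step 4. Why the table is not enough.** Take n = 6 and an assumed geometric CV of 40% in both columns, so s = √ln(1 + 0.40²) = 0.385. The SD of the paired log difference is s√(2(1 − ρ)), where ρ is the within-subject fed–fasted correlation, which the table does not show. The 90% CI is the ratio ×/÷ exp(t(0.95, 5) · SD/√6), with t = 2.015.

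| ρ | 0 | 0.5 | 0.8 | 0.9 |
|---|---|---|---|---|
| CI factor | 1.57 | 1.37 | 1.22 | 1.15 |

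The same printed table is compatible with all four intervals.

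**Step 5. Precision if the model is restored.** The plan gives no food-effect precision or power figure to reproduce. For n complete pairs, the 90% CI is the ratio ×/÷ exp(t(0.95, n − 1) · σ · √(2/n)), where σ = √ln(1 + CV²) and CV is the within-subject CV. An assumed CV of 15% gives σ = 0.149, and 30% gives σ = 0.294.

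| Evaluable pairs | t | CV 15% | CV 30% |
|---|---|---|---|
| 6 | 2.015 | 1.19 | 1.41 |
| 5 | 2.132 | 1.22 | 1.49 |
| 4 | 2.353 | 1.28 | 1.63 |
| 3 | 2.920 | 1.43 | 2.01 |

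Worked case, n = 6 and CV 30%: exp(2.015 × 0.294 × √(2/6)) = exp(0.342) = 1.41. Around a true ratio of 1.00, that is 0.71 to 1.41.

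**The case against.** The strongest case is that this is a disclosed reduction of scope after early termination. SAP Section 10 lists the change openly, and protocol 10.3.1 sends the justification of deviations to a separate document and the CSR, neither of which is available here. This stands, and no fault is claimed in the SAP for printing no reason. The SAP does not itself link this omission to the termination.

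A second argument is that the objective is only to investigate, with no hypothesis, margin or formal sample size, so description may suffice, and SAP 6.2 declares statistical tests not applicable. However, a ratio with a CI is estimation, not a test. SAP 8.3.3 keeps a regression with 95% CIs for dose proportionality, so a reader should not infer that model-based estimation was abandoned altogether. The protocol chose the ratio and interval while planning at most six active subjects in Part 2.

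Third, the surviving objective is weak evidence taken alone. The SAP says that assessments not performed are greyed out, and shading may be lost in text extraction. The gender objective also still reads as live although Part 4 never enrolled. This too stands. The firmer evidence is that Part 2 was run.

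Fourth, the sample is small and its usable size unknown. Table 1 of the protocol allocates 6 active to 2 placebo, so any six of those eight include at least four on active drug. A reader might infer at least four pairs. The documents do not support that, because the PK analysis set (SAP Section 5) also requires study completion, no major emesis within 2 hours of dosing and evaluable parameters. A wide interval would be a reason to show the uncertainty.

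**Conclusion.** The point holds as a missing estimate. Part 2 was carried out, and the only planned fed/fasted geometric mean ratio and CI was removed, with only description in its place. The textual part rests on no assumption. The sizes do: the within-subject CV (15% to 30%), the 40% geometric CV, the correlations and the number of evaluable pairs are all assumed. The restored interval would be imprecise, between ×/÷ 1.19 and ×/÷ 2.01 over the cases tabulated. The matter deserves correction but is not critical: it concerns a secondary objective and leaves the primary safety analysis untouched.

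Two stronger readings are tempting. One is that the fasted column will include subjects who did not return, which would distort even a crude ratio. SAP 9.2 does not say who is in that column. Two Part 1 cohorts had six subjects each, and if one of them supplied Part 2, all of it returned. The other is that AUC0-last is biased because the Part 2 cohort skips the Part 1 Follow-up Visit, where the last PK sample is taken (protocol 5.2.4.1). Any effect depends on a half-life and a quantification limit that the documents do not give, and it is a separate sampling question. Neither is part of this finding.

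**What to change.** Delete the mixed-model bullet from SAP Section 10 and add a food-effect paragraph to SAP 8.3, for example:

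*Log Cmax, log AUC0-∞ and log AUC0-last from active subjects with evaluable PK in both periods will be analysed in a linear mixed model (fixed effect: fed state; random effect: subject). The fed/fasted geometric mean ratio and its 90% CI will be reported as exploratory, together with the number of pairs.*

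If the database is already locked, report the same analysis as exploratory in the CSR.

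The cost is one model and one table on data already collected, with no new procedures. Since Section 10 says the analysis was not done, it must be run and reported as well as written into the SAP. The interval will be wide. All subjects took the fasted period first, so food cannot be separated from period. That limitation applies equally to the descriptive comparison and is a reason for the exploratory label.
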